7.6.3.5 Technetium-99m Scintigraphy Parameters

Descriptive statistics of actual value and change from baseline for selecteechnetium-99m Scintigraphy parameters will be generated for each treatment group by visit.

Note: This procedure is only at selected sites. A summary of the sites that had the capabilities to perform the test will be tabulated.

7.6.3.6 Amyloid in Abdominal Wall Fat Pad Aspirates

Tabulations of result of test and grade of test will be generated for each treatment group by visit.

Note: This procedure is voluntary for the patients. A summary of sites where patients volunteered for this procedure will be tabulated.

7.6.3.7 Polyneuropathy Disability Score

PND score will be categorized into 4 categories:

- Category 1: Stage 0=No symptoms
- Category 2: Stage I=Sensory disturbances but preserved walking capabilities or Stage II=Impaired walking capacity but ability to walk without a stick or cane,
- Category 3: Stage IIIA=Walking with the help of one stick or crutch or Stage IIIB=Walking with the help of two sticks or crutches
- Category 4: Stage IV=Confined to a wheelchair or bedridden.

Descriptive statistics of a shift from baseline PND category [range: categories 1 -4] to post-baseline PND category [range: categories 1-4] at each follow-up visit will be presented by treatment group.

Additionally, the number of patients and associated percentage of each PND score stage at each visit will be presented by treatment groups.

7.6.3.8 Modified Body Mass Index

Modified body mass index is defined as Body Mass Index (BMI) multiplied by albumin level collected at the same visit.

Descriptive statistics of actual value, change from baseline and percent change from baseline for modified BMI will be generated for each treatment group by visit.

Descriptive statistics of actual value, change from baseline and percent change from baseline for eGFR (mL/min/1.73 m^2) will be generated for each treatment group by visit. Additionally, categorical shifts in eGFR [(\geq 15-30), (\geq 30-60), (\geq 60-90), \geq 90)] from baseline to worst post-baseline eGFR category will be generated for each treatment group.

7.6.3.10 Heart Failure (HF) Hospitalization

7.6.3.9 Estimated Glomerular Filtration Rate (eGFR)

The time from date of first dose of study drug to HF hospitalization will be a stratified Cox proportional hazard model using Anderson-Gill method to model recurrent events. To account for the correlation of CV events within each subject the Cox proportional hazards model will specify a robust sandwich estimate for the covariance matrix. The hazard ratio and associated 95% confidence interval of the hazard ratio will be presented.

The cumulative number of HF hospitalizations per patient reported during each visit intervals [>0 to \leq 6 months, >6 to \leq 12 months or >12 to \leq 18 months and >0 to \leq 18 months] will be presented for each treatment group. Additionally, at each visit interval, the cumulative number of HF hospitalizations and percentage of patients with a HF hospitalization event will be tabulated.

7.6.3.11 EO-5D-5L

Descriptive statistics of Index score (US reference), and VAS at baseline will be presented by treatment groups at each visit. For each of the 5 dimensions (Mobility, Self-Care, Usual Activities, Pain/Discomfort, Anxiety/Depression), a frequency (and associated percentage) of the number of patients who reported the levels of symptom will be presented by treatment group at each visit. Change from baseline in each of the summary scores (Index score and VAS) will be presented for each treatment group. For each of the 5 dimensions, a shift table of baseline to worst post-baseline shift of symptoms of the EQ-5D questionnaire will be presented by treatment group.

Additional details of the EQ-5D-5L questionnaire are located in Appendix V.

7.6.3.12 Pharmacoeconomic Questionnaire (PEQ)

Frequency (percentage) of the following parameters will be summarized by treatment group and visits:

- Number (No.) of Visits to General Practitioner
- No. of Visits to Specialist Physician in less 6 months
- No. of Visits to the ER in the last 6 months due to FAC
- Level of Function categories (eg, able to work full time and live at home, unable to work)
- Symptoms experienced in the last month
- Caregiver ability to retain a job

A per patient listing will also be generated of the responses to the PEO questionnaire.

7.7 Safety

All safety analyses will be analyzed using the Safety Population. The safety analysis will be summarized by the treatment that was actually received. If a patient received at least one dose of revusiran, he/she would be grouped in the revusiran arm for safety analyses.

7.7.1 Adverse Events

All safety analyses will be based on treatment emergent adverse events (AEs) and will be summarized by treatment received. A treatment-emergent AE is defined as any AE occurring or worsening in severity after the first dose (including date/time) of study drug administration through 28 days after the last dose, or any event that was present at baseline but worsened in intensity or was subsequently considered drug-related by the Investigator. AEs will be summarized using the Medical Dictionary for Regulatory Activities (MedDRA Version 17.1 or later) by System Organ Class (SOC) and Preferred Term (PT). All treatment emergent AEs hereafter will be referred to as AEs in this document.

An overview of the frequency (percentage) of AEs will be tabulated (such as but not limited to, the number of patients with at least 1 AE related to study drug, the number of patients with a severe AE, the number of patients with at least 1 SAE, and the number of patients who discontinued study drug due to an AE). Separate tabulations will be produced for all AEs, AEs by maximum severity, treatment-related AEs by severity, serious adverse events (SAEs), discontinuation from study drug due to AEs and deaths. These tabulations will be presented by SOC and PT. In addition, a summary table of all AEs and SAEs sorted by decreasing frequency based on PT for each treatment group will be generated. Any AEs leading to discontinuation of study drug, death and any SAEs will be presented in patient listings.

Additional summary tables of AEs by SOC and PT per treatment group include the following:

- Frequent SAEs [defined as SAEs occurring in ≥5% in either treatment group]
- Frequent AEs [defined as AEs occurring in ≥ 10% in either treatment group]
- CV Hospitalizations*
- CV Mortality*
- HF Hospitalizations*

*Note: The classification of death and hospitalization events will be determined by an independent Clinical Adjudication Committee (CAC).

Event of Special Interest: Injection Site Reactions [ISRs]. ISRs are defined as any AEs which maps to the HLT='Injection Site Reactions' using MedDRA dictionary.

The following summary will be generated by treatment group:

- Frequency (percentages) of ISRs by HLT and PT
- Frequency (percentage) of ISRs by maximum severity, HLT and PT
- Listing of study drug discontinuation due to an ISR

No formal hypothesis-testing analysis of AE incidence rates will be performed.

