4.3. Study Drug Discontinuation

The Investigator or designee may discontinue dosing in a patient if the patient:

- Is in violation of the protocol
- Experiences a serious or intolerable AE
- Is found to be considerably non-compliant with the protocol-required visits

The Investigator will confer with the Sponsor or CRO Medical Monitor before discontinuing dosing in the patient. Patients who are pregnant will be discontinued from dosing immediately.

Patients who discontinue study drug for any reason will be encouraged to remain on the study and complete their remaining clinic visits through the 18-month visit. Patients who discontinue study drug may receive local standard of care treatment for their disease.

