8.5. Adverse Event Reporting Period

AEs and SAEs will be reported according to the following timeframes:

 For patients who complete the study, AEs will be assessed through the End of Study Visit, Week 82. All AEs that occur after the start of study drug administration on Day 0 must be reported in detail on the appropriate eCRF page and followed to satisfactory resolution, or through the End of Study Visit after the last dose of study drug administration. Serious AEs will be followed through the End of Study Visit, or

until satisfactory resolution, or until the SAE is considered by the Investigator to be chronic or the patient is stable.

For patients who withdraw from the study early, ongoing AEs will be followed until
resolution or 28 days from last dose, whichever occurs first. Serious AEs will be
followed through 28 days from the last dose of study drug, or until satisfactory
resolution, or until the SAE is considered by the Investigator to be chronic or the
patient is stable.

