9.2.4. Safety Analyses

Adverse events will be summarized by MedDRA system organ class and preferred term. Separate tabulations will be produced for all treatment emergent AEs, treatment-related AEs (those considered by the Investigator as at least possibly drug related), SAEs, and discontinuations due to AEs. By-patient listings will be provided for deaths, SAEs, and events leading to discontinuation of treatment.

Descriptive statistics will be provided for clinical laboratory data and vital signs data, presented as both actual values and changes from baseline relative to each on-study evaluation and to the last evaluation on study.

Descriptive statistics will be provided for ECG interval data and presented as both actual values and changes from baseline relative to each on-study evaluation and to the last evaluation on study. Details of any abnormalities will be included in patient listings.

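### The SAP's adverse event tables, including those for SAEs and deaths, leave out new-onset events starting more than 28 days after the last dose, although these are collected from patients followed off drug

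*SAP*

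**What the plan says.** SAP 7.7.1 sets the basis for the adverse event analyses: "All safety analyses will be based on treatment emergent adverse events (AEs) and will be summarized by treatment received". An event is treatment-emergent if it occurs or worsens from the first dose of "study drug administration through 28 days after the last dose". A second limb then adds "or any event that was present at baseline but worsened in intensity or was subsequently considered drug-related by the Investigator", with no end date. The section closes the definition with a naming rule: "All treatment emergent AEs hereafter will be referred to as AEs in this document". The tables that follow under this rule cover all AEs, SAEs, events leading to discontinuation, and deaths. Further AE tables cover CV hospitalizations, CV mortality and HF hospitalizations.

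The protocol collects data over a longer period. Under Protocol 4.3, patients who stop study drug "will be encouraged to remain on the study and complete their remaining clinic visits through the 18-month visit". Under Protocol 8.5, "For patients who complete the study, AEs will be assessed through the End of Study Visit, Week 82", and for these patients the duty to report events after dosing starts on Day 0 has no cut-off tied to the last dose.

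Protocol 9.2.4 attaches the treatment-emergent qualifier to the all-AE tabulation only. It names SAE tabulations separately and adds: "By-patient listings will be provided for deaths, SAEs, and events leading to discontinuation of treatment".

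**The concern.** The safety tables use a shorter window than the data collection. For a patient who stops drug early and stays on study, a new SAE more than 28 days after the last dose reaches the database but not the SAE table. A fatal event in that period is likewise outside the death table of the safety section.

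The SAP expects such patients. Section 7.2 counts those who stopped treatment and completed their remaining visits, and section 7.4.2 summarizes medications started after the last dose. No corresponding summary is planned for SAEs.

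The definition is also uneven. Because its second limb is open-ended, a late worsening of heart failure present at baseline can count as treatment-emergent, while a late new event of equal seriousness cannot.

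At stake is the completeness of the serious-event comparison between arms. The report could also give different CV death and hospitalization counts in its efficacy and safety sections without explaining why.

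**Working it through.** **Window against collection period.** The last scheduled dose is at Week 78 (Protocol Table 1-1), and 78 + 28/7 = 82. A patient dosed to the end loses nothing. A patient who stops at week w and stays on study has a window ending at w + 4, which leaves 82 - (w + 4) collected weeks outside it.

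| Last dose | Window ends | Weeks outside, to Week 82 |
|---|---|---|
| Week 13 | Week 17 | 65 |
| Week 26 | Week 30 | 52 |
| Week 52 | Week 56 | 26 |
| Week 65 | Week 69 | 13 |

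**Where a late new-onset event appears (SAP).**
- SAE, death and CV/HF event tables in 7.7.1: not included.
- Deaths to Month 18: included under efficacy in 7.6.2.6, by type (CV, HF, neither).
- CV deaths and CV hospitalizations to Month 18: included in 7.6.2.1. HF hospitalizations: included in 7.6.3.10.
- Any other non-fatal SAE: no table.

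**Illustration for deaths.** Inputs from the plan are 18-month mortality of 13% on revusiran and 20% on placebo (SAP 2.3) and about 200 patients randomized 2:1, so about 133 and 67. Expected deaths are 133 × 0.13 = 17.3 and 67 × 0.20 = 13.4. Three inputs are assumptions: a constant hazard, the share q who stop drug but stay on study, and when they stop.

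*Stopping times uniform over 78 weeks.* With weekly hazard λ, survival S(t) = exp(-λt) and stopping time U, a stopper's death falls outside the window if it occurs after U + 4 and by Week 78. The probability is

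[S(4) - S(78)]/(78λ) - (74/78) × S(78).

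Revusiran: 78λ = -ln(0.87) = 0.1393 and S(4) = 0.9929, so (0.9929 - 0.87)/0.1393 - 0.9487 × 0.87 = 0.882 - 0.825 = 0.057.
- q = 10%: 13.3 × 0.057 = 0.8 deaths.
- q = 20%: 26.6 × 0.057 = 1.5 deaths.

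Placebo: 78λ = -ln(0.80) = 0.2231 and S(4) = 0.9886, so (0.9886 - 0.80)/0.2231 - 0.9487 × 0.80 = 0.845 - 0.759 = 0.086.
- q = 10%: 6.7 × 0.086 = 0.6 deaths.
- q = 20%: 13.4 × 0.086 = 1.2 deaths.

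*All stopping at Month 6 (revusiran).* The monthly hazard is -ln(0.87)/18 = 0.00774. The time outside the window is 18 - (6 + 28/30.4) = 11.08 months. The risk of death in that time is 1 - exp(-0.00774 × 11.08) = 8.2%, which gives 13 × 0.082 = 1.1 deaths at q = 10% and 27 × 0.082 = 2.2 at q = 20%.

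Both patterns give about 1-2 of about 17 revusiran deaths. These are upper bounds, because they treat every late death as outside the definition although some may qualify through the open-ended second limb. With equal stopping rates the arms lose a similar share of deaths: at 10%, 0.8/17.3 and 0.6/13.4, each about 4%.

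**The case against.** The strongest reply is that a 28-day window is conventional and fits this design. It matches the Week 78 to Week 82 follow-up and the 28-day follow-up of events in early withdrawals (Protocol 8.5). Patients off drug may receive local standard of care, which blurs attribution of late events. This justifies keeping the treatment-emergent tables. It does not justify having no whole-study table of serious events alongside them.

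A reader might infer four stronger points, none of which the documents support.

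- *Every safety analysis is cut off.* The sentence in 7.7.1 reads that way, but SAP 7.7.2, 7.7.4 and 7.7.5 run laboratory, liver test, vital-sign and ECG summaries by visit or on post-baseline values without using treatment-emergent status. A late hepatic signal would still show in the liver test tables.
- *Late SAEs and deaths also leave the listings.* This is ambiguous. SAP 7.1 lists all collected data unless otherwise specified, and the listing sentence in 7.7.1 refers to any SAEs. The naming rule in 7.7.1 points the other way.
- *Late deaths vanish from the report.* They do not: the efficacy summaries count them by arm and type. The mITT and safety populations are essentially the same dosed patients, differing mainly in grouping as randomized or as treated. Those summaries are not by system organ class and preferred term, however, and do not cover other SAEs.
- *The cut-off hides harm in the revusiran arm in particular.* Injection site reactions and liver test rises led some patients to stop revusiran (Protocol 1.3, 1.6.1, 1.6.2), so a greater loss there is plausible. But no stopping rate by arm is given, Protocol 6.6 allows dose reduction and re-challenge, and Protocol 5.6 notes such reactions on placebo too.

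**Conclusion.** The point holds as a gap in the safety tables. New-onset SAEs and fatal events starting more than 28 days after the last dose are collected from patients followed off drug but are not in the SAP's AE, SAE, death or CV/HF event tables. Those that are neither fatal nor CV/HF hospitalizations have no table anywhere. The SAP is narrower here than Protocol 9.2.4, and the two limbs of its definition end at different times.

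The size is modest. At assumed stopping rates of 10-20%, at most about 1-2 of about 17 expected revusiran deaths miss the safety death table, and they remain visible under efficacy. The number of other SAEs lost cannot be estimated, because the documents give neither an SAE rate nor a stopping rate. Harm to the between-arm comparison is possible but not demonstrated. This is a worthwhile, inexpensive improvement to the SAP.

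**What to change.** Keep the treatment-emergent tables and amend SAP 7.7.1 in three ways.

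1. Add tabulations by arm of all SAEs, all fatal AEs, and adjudicated CV deaths and CV/HF hospitalizations from first dose to end of study, regardless of the last dose date.
2. State that the by-patient death and SAE listings are unrestricted, with each event flagged as on or off treatment.
3. Give both limbs of the treatment-emergent definition the same end date.

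The cost is SAP wording and a few extra tables from data already collected. The downside is that off-drug events add background disease noise, which the flag lets the reader separate.

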	Consented eligible patients will be randomized to receive either 500 mg ALN-TTRSC or placebo in a 2:1 ratio (ALN-TTRSC:placebo) in a blinded manner. Treatment groups will be balanced at entry for New York Heart Association (NYHA) classification (I and II vs III), TTR mutation (V122I versus other FAC mutations), and Screening/Baseline 6-minute walk distance (6-MWD [≤325 meters vs >325 meters]). Patients will receive ALN-TTRSC or placebo for 5 daily doses during the first week and then once every week for approximately 18 months. Patients will return to clinic for a follow-up visit approximately 4 weeks after their last dose of study drug.
	Patients will undergo efficacy and safety assessments at Screening/Baseline, each month for first 3 months and then at 3-6 month intervals. In addition, pharmacokinetics (PK) of ALN-TTRSC and its effect on quality of life and pharmacoeconomics will be characterized at selected time points.
	Eligible patients who complete study dosing and the 18 month efficacy assessments may be eligible to participate in a ALN-TTRSC open-label extension study.
	An independent Data Monitoring Committee (DMC) will be implemented for the study and will operate under a prespecified charter.
	An independent Clinical Adjudication Committee (CAC) will adjudicate the secondary endpoints of mortality and hospitalization.
Study Sites	This study is to be conducted at approximately 60 study sites worldwide.
Investigational Drug	ALN-TTRSC is comprised of a small interfering ribonucleic acid (siRNA) targeting mutant and wild-type (WT) TTR messenger RNA (mRNA) with a covalently attached N-acetylgalactosamine (GalNAc) ligand formulated in water for injection.
Dosage, Route of Administration and Duration of Treatment of Investigational Drug	Patients randomized to ALN-TTRSC will receive 5 daily subcutaneous (SC) injections of 500 mg of ALN-TTRSC (Day 0 through Day 4). The same dose will be administered at Day 7 and then once weekly through 18 months.
Control Drug	Placebo (normal saline 0.9% for SC administration). Placebo will be packaged and administered identically to ALN-TTRSC.
Dosage, Route of Administration and	Patients randomized to placebo will receive SC normal saline (0.9%) using the

Duration of Treatment of Control Drug	same dosing schedule as the active treatment group.

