ALN-TTRSC-002 was an open-label, multiple-dose Phase 2 study of ALN-TTRSC administered to patients with ATTR cardiac amyloidosis. Patients received ALN-TTRSC 5 mg/kg or 7.5 mg/kg for 10 doses over a 35 day period administered as 5 daily SC doses followed by 5 weekly doses. Multiple doses of ALN-TTRSC were generally well-tolerated. The majority of AEs were mild or moderate in severity, not related to study drug and expected for the population under study. Three patients experienced 1 SAE each, 2 of which were unrelated to study drug (non-cardiac chest pain and implantable defibrillator insertion). The third SAE was asymptomatic elevation of ALT (4.2×ULN) and AST (3.2×ULN) after administration of 6 doses of 5 mg/kg ALN-TTRSC and was considered mild in severity and possibly related to study drug. Study drug was interrupted for 1 dose and then resumed with subsequent normalization of ALT and AST during the remaining period of dosing. The most common AEs related to study treatment were ISRs which were localized, mild in severity, self-limiting and did not result in interruption or dose reduction. A PD effect of >85% TTR reduction with 5 mg/kg or 7.5 mg/kg ALN-TTRSC dosing was observed.

ALN-TTRSC-003 is an ongoing, Phase 2 open-label extension study to evaluate long-term treatment with ALN-TTRSC for patients who completed the ALN-TTRSC-002 study. Patients receive ALN-TTRSC 500 mg administered as 5 daily SC doses, followed by weekly SC doses for approximately 2 years. As of 05 January 2016, 25 patients have been treated with ALN-TTRSC for approximately 8 months (range 1-13 months). Multiple doses of ALN-TTRSC have been generally well-tolerated. The majority of AEs were mild or moderate in severity. The most common AEs related to study drug have been ISRs, usually characterized by transient

erythema, pruritus, pain, or swelling at or around the injection site. Occasionally, these reactions have been recurrent, of longer duration and increased intensity. In some cases, ISRs have led to interruption or discontinuation of study drug. Elevations of ALT and AST have been observed, the majority of which have been mild, transient, <3×ULN and not associated with any changes in total bilirubin or clinical symptoms. In several subjects, the elevations may have led to interruption and/or dose reduction of study treatment. There were no serious hepatic AEs.

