1.6.1. Injection Site Reactions

ISRs have been observed in subjects receiving ALN-TTRSC in clinical studies. The majority have been mild or moderate in severity. Typically, the reactions consist of localized erythema, pain, swelling, pruritus, or rash at or around the injection site, and are transient in nature. Occasionally, these reactions have been of longer duration, more severe in nature and/or recurrent. In some subjects, this resulted in discontinuation of ALN-TTRSC. If such reactions occur, rotation of the injection site (e.g., to the extremities) is recommended as a potential mitigation strategy (see Section 6.5). Dose reduction may be considered in some cases after consultation with the Medical Monitor (see Section 6.6).

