6.6. Dosing Modification Criteria

During the study, if a patient has an elevation of AST, ALT, or total bilirubin (unless due to Gilbert's Syndrome) $>3\times$ ULN, repeat assessments of AST, ALT, and total bilirubin should be performed within 72 hours. The patient should be followed closely, with LFT assessments performed weekly, and as medically indicated to guide patient management. Close monitoring may be discontinued when ALT, AST, and total bilirubin return to $\leq 3\times$ ULN. Additional, and repeat assessments, may be performed at the discretion of the Investigator.

Dosing will be held for the following LFT abnormalities:

- AST or ALT elevation of ≥3×ULN in association with either total bilirubin elevation of ≥1.5×ULN or gastrointestinal symptoms including nausea, vomiting, and/or abdominal pain
- AST or ALT elevation of >5×ULN

Under these circumstances the contract research organization (CRO) Medical Monitor and Investigator, in consultation with a hepatologist as deemed necessary, will decide on appropriate action regarding frequency of repeat LFTs and resumption of dosing.

If a patient experiences an AE considered to be related to study drug, and the Investigator has any potential concerns with regard to further dosing, the Medical Monitor and Investigator will review all available safety data for the patient. Based on this review, it may be determined that further administration of study drug will be discontinued or study drug administration at the same dose may resume.

If a patient has recurrent or severe ISRs, or clinically significant LFT abnormalities, the Investigator and the Medical Monitor should determine whether the patient is a candidate for a dose reduction of study drug. In suitable candidates, dose reduction to 250 mg ALN-TTRSC (or placebo equivalent) is allowed. In patients who have been dose reduced, subsequent re-challenge at the full dose may be considered based on the judgment of the Investigator and Medical Monitor.

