8.4. Adverse Event Reporting

The Investigator is responsible for reporting all AEs that are observed or reported after the first dose of study drug regardless of their relationship to study drug through the end of the reporting periods defined in Section 8.5.

Any medical condition that is present when a patient is screened and does not deteriorate should not be reported as an AE. However, if it does deteriorate at any time after the first dose of study drug, it should be reported as an AE.

All AEs must be fully recorded in the site's source records and in the patients' eCRF, whether or not they are considered to be drug-related. Each AE should be described in detail: onset time and date, description of event, severity, relationship to investigational product, action taken, and outcome (including time and date of resolution, if applicable).

For AEs that are considered AEs of clinical interest, additional clinical information may be collected based upon the severity or nature of the event. If a patient has ISRs meeting any of the following criteria, the Investigator, or delegate, should contact the Medical Monitor and submit a supplemental ISR eCRF:

- ISRs that are recurrent and/or demonstrate a pattern of increasing severity
- Any ISR that is determined to be severe and/or a cause for study drug discontinuation
- Any ISR which, in the opinion of the Investigator, requires further medical evaluation or treatment

In some cases, where it is medically appropriate, further evaluation may include photographs, referral to a dermatologist, skin biopsy, or other laboratory testing. If a biopsy was obtained, the Sponsor may request that the biopsy also be reviewed by a central dermatopathologist.

For patients with hepatic AEs, local laboratory results may be collected to monitor LFT levels or other laboratory parameters.

Refer to the CRF completion guidelines for details on reporting events in the supplemental AE of
clinical interest eCRF form(s). When the form(s) is/are completed,
personnel will be notified electronically and may

follow-up with queries.

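### Injection site reactions are summarised by arm only as patients affected and by worst grade, so repeat reactions over 83 scheduled injections, their duration, and doses held or reduced for them are not shown

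*SAP*

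**What the plan says.** **Analysis.** SAP 7.7.1 makes ISRs an event of special interest. It plans frequency and percentage by high-level and preferred term, then "Frequency (percentage) of ISRs by maximum severity, HLT and PT", then "Listing of study drug discontinuation due to an ISR". SAP 7.1 makes patients in the analysis population the default denominator unless the table shells say otherwise. The general tables in SAP 7.7.1 cover all adverse events, events by maximum severity, treatment-related events by severity, serious events, and discontinuations due to adverse events, all by system organ class and preferred term. SAP 7.5 summarises treatment duration and number of doses received.

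**Risk.** Protocol 1.6.1 says of ISRs: "Occasionally, these reactions have been of longer duration, more severe in nature and/or recurrent". Protocol 1.3 says of the open-label extension: "Occasionally, these reactions have been recurrent, of longer duration and increased intensity". It adds that some ISRs there led to interruption or discontinuation of drug. For recurrent or severe ISRs, or clinically significant liver test abnormalities, protocol 6.6 states: "In suitable candidates, dose reduction to 250 mg ALN-TTRSC (or placebo equivalent) is allowed".

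**Data collected.** Protocol 8.4 requires onset, severity, action taken, outcome and resolution date for each adverse event. It also requires a supplemental ISR form, and one of its triggers is "ISRs that are recurrent and/or demonstrate a pattern of increasing severity". Protocol 8.7 asks for the start and stop of each occurrence of an intermittent event, and for a separate dated record when severity changes over days.

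**The concern.** The protocol describes the ISR risk largely by its course: repeated, longer, more intense, and at times disrupting treatment. The planned ISR tables count a patient once per term or once at the worst grade. A patient with one mild reaction and a patient with a mild reaction after most injections fall in the same cell. Protocol 5.6 says that placebo injections also cause ISRs, so the informative result is the contrast in burden between arms, and a count of patients ever affected may show little of it. A reader judging tolerability of long-term weekly dosing would have no by-arm summary of recurrence, duration, or treatment interrupted or reduced because of an ISR.

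**Working it through.** The plan states no ISR rate or ISR precision figure, so there is no figure of its own to reproduce. The check has two parts.

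**1. Do the planned outputs show the features that the protocol names?**

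| Feature | Where the protocol raises it | Shown by arm in the SAP? |
|---|---|---|
| Peak severity | 1.3, 1.6.1 | Yes, ISRs by maximum severity |
| Discontinuation | 1.3, 1.6.1 | Yes, general discontinuation table by preferred term; also the ISR listing |
| Recurrence, number of reactions | 1.3, 1.6.1, 6.6, 8.4 | No |
| Duration | 1.3, 1.6.1 | No |
| Rising severity over time | 8.4 | Only as the peak reached, not the course |
| Interruption or dose reduction because of an ISR | 1.3, 1.6.1, 6.6 | No |

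SAP 7.5 does not close the last gap. It counts doses without dose level or reason, so a reduced dose still counts as one dose, and a missed dose is not linked to its cause. The per-protocol rule in SAP 5.3.1 also counts doses. Protocol 9.2.4 adds none of the missing summaries, and the SAP never mentions the supplemental ISR form. By contrast, SAP 7.6.2.1 and 7.6.3.10 do specify cumulative event counts per patient for hospitalisations.

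**2. How much can a percentage ever affected hide?**

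Inputs: 5 daily injections on Day 0 to Day 4 (protocol synopsis); then "The same dose will be administered at Day 7 and then once weekly through 18 months", with dosing marked at Week 78 in Table 1-1, so 78 weekly doses. At one injection per dose the total is 5 + 78 = 83.

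Assumption, not from the documents: each injection carries the same ISR probability q, independently, in every patient, and all 83 are given. Then:

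- proportion ever affected = 1 − (1 − q)^83
- mean reactions per patient = 83q

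| q | Ever affected | Reactions per patient |
|---|---|---|
| 1% | 56.6% | 0.83 |
| 3% | 92.0% | 2.49 |
| 5% | 98.6% | 4.15 |
| 10% | 99.98% | 8.30 |

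So 3% versus 10%, a 3.3-fold difference in reactions (8.30 / 2.49), would appear as 92% versus about 100%.

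Now assume instead that only 30% of patients are susceptible in both arms, with q applying to them alone. Ever affected = 0.30 × [1 − (1 − q)^83]; reactions per 100 patients = 100 × 0.30 × 83q.

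| q among susceptible patients | Ever affected | Reactions per 100 patients |
|---|---|---|
| 3% | 27.6% | 74.7 |
| 5% | 29.6% | 124.5 |
| 10% | 30.0% | 249 |
| 30% | 30.0% | 747 |

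Here the percentage stays near 30%, far from its ceiling, yet 5% versus 30% is a six-fold difference in reactions that it does not show.

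**The case against.** The strongest reply is that this is standard adverse event reporting, purely descriptive, with formal testing of incidence rates ruled out by SAP 7.7.1. More tables can be added at any time from data already held. The overview there is expressly not exhaustive, SAP 7.1 promises listings of all collected data by treatment group, and the table shells are not part of the documents. The SAP (21 October 2015) was also written from protocol 1.0 of 3 October 2014, whereas the current protocol cites January 2016 data. We cannot tell whether protocol 1.0 contained the dose-reduction provision or the supplemental form, so the gap may be an update that is due rather than a choice. All of this stands, and it keeps the point minor. It does not remove the gap: a listing or an optional table is not a prespecified by-arm summary.

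A reader might also infer four stronger things that the documents do not support:

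- *That the ISR harm will appear in no by-arm result.* Peak severity and ISR discontinuations do appear by arm, and missed doses show in aggregate.
- *That dose reduction is a known consequence of ISRs.* The protocol permits it. For ISRs it reports interruption or discontinuation; the reductions mentioned in 1.3 concern liver enzyme elevations, and in the completed Phase 2 study ISRs led to neither interruption nor reduction.
- *That the percentage must saturate in both arms.* That depends on independent injections and equal risk across patients. The protocol describes recurrence as occasional, which points to clustering. If the arms differ in the share of patients who react at all, the planned table will show it.
- *That ISRs would be misreported.* Incidence and worst grade would be correct, but incomplete.

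**Conclusion.** The concern holds in a limited form and is minor. No planned by-arm summary shows repeat ISRs, their duration, or study drug interrupted or reduced because of an ISR, although the protocol treats these as part of the risk and collects data on them. That conclusion rests on reading the two documents together, with the patient as the unit of count under SAP 7.1, and needs no rate assumption.

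The size is illustrative only. The figure of 83 is the schedule; deaths, withdrawals and missed doses will lower it. Every per-injection rate above, and the 30% susceptible share, is assumed. What is common to both illustrations is that a several-fold difference in reaction count can sit behind similar percentages ever affected. No efficacy conclusion or error rate depends on this.

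**What to change.** Update SAP 7.7.1 to the current protocol and make these additions before unblinding.

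1. **Define an ISR episode.** Merge contiguous severity-change records (protocol 8.7), and merge concurrent preferred terms arising from the same injection. Without this rule, one reaction with redness, pain and swelling, or one that changes grade, would be counted several times.
2. **Add descriptive tables by arm:**
   - ISR episodes per patient and per 100 injections received;
   - distribution of episodes per patient, with categories fixed before unblinding;
   - episode duration;
   - patients whose supplemental form was triggered by recurrence or increasing severity, kept apart from the other triggers in protocol 8.4 (a severe reaction, one causing discontinuation, or one needing further evaluation or treatment), because a count of all forms would not measure recurrence;
   - patients with ISRs leading to interruption, dose reduction or discontinuation, taken from the action-taken field once it is confirmed that the field separates these.

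The cost is one derivation rule, a few tables and the SAP wording. It needs no new data collection, spends no alpha and changes no clinical rule. SAP 7.8 already foresees a SAP update for the futility criteria, and protocol 9.2 has the SAP finalised before database lock, so the change can go into the same revision.
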